#### 5.3.6 Boost Doses

Additional boost doses may be given through reduced field to persistent tumor and/or clinically positive nodes, or to compensate for significant interruptions in radiation therapy treatments (i.e., > 57 elapsed days). The additional boost dose should not exceed 4 Gy (i.e., 70 Gy maximum). The spinal cord must be excluded from any boost field.

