### 5.3.3 Radiation Dose

Treatment to the primary tumor and upper neck will be given at 2 Gy/fraction once each day, five days a week. A total dose of 70 Gy/35 fractions/7 weeks will be delivered. Fields must be reduced to exclude the spinal cord at 36 Gy with dose calculated in the central plane. The entire neck must be irradiated to a total dose of at least 46- 50 Gy (even in N0 stage) at anatomic levels of lymph nodes usually 2-4 cm beneath the skin surface. Clinically positive neck nodes should also receive a dose of 70 Gy/35 fractions given continuously for 7-8 weeks. An electron beam should be used to supplement the dose to the posterior cervical chain nodes after the spinal cord has been shielded. Hence, the total dose to the primary tumor and clinically positive nodes will be 70 Gy. The anterior lower neck will be treated at 2 Gy/fraction once a day (3 cm depth or at depth determined by 3D imaging) from the anterior to a total dose of 46-50 Gy/25 continuous fractions (if clinically negative) in 5 weeks. The maximum dose permitted to the spinal cord will not exceed 45 Gy as determined by a separate off-axis point dose calculation.

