#### 5.3.4.2 Upper Neck Primary Volume

The primary treatment fields should encompass the primary tumor and/or suspected lymph node disease in the upper neck using the shrinking field technique as follows:

The initial target volume should include the primary tumor, positive nodes with an approximately 3.0 cm margin and the next echelon of uninvolved lymphatic nodal drainage sites to a dose of 50 Gy. Included in the target volume is the first field reduction occurring off the spinal cord at 36 Gy.

The second field reduction will occur at 50 Gy and continue to 60 Gy with the new target volume encompassing the primary tumor and known areas of nodal disease as well as areas at high risk for lymph node involvement with approximately 2.0 cm margin.

The third and final field reduction will occur at 60 Gy and continue to 70 Gy with the new target volume encompassing the primary tumor and known areas of nodal disease with at approximately 1.0 cm margin.

As a general rule, both ipsilateral and contralateral posterior cervical nodal chain and the adjacent echelon of uninvolved lymphatic nodal drainage sites will be treated to a dose of 46-50 Gy/5 weeks.

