5.3.11.2 Radiation Target and Dose Specifications

The following is the definition of targets and their dose specifications.

Primary Target (PTV3): Includes PTV's of primary tumor and the lymph nodes containing disease. The dose will be 70 Gy at 2 Gy/ fractions.

Secondary Target (PTV2): Includes PTV's of area at moderate to high risk of microscopic disease i.e. first echelon nodes. The dose will be 60 Gy.

Tertiary Target (PTV1): Includes PTV's of areas that are at low risk of microscopic disease i.e. second echelon lymph nodes. The dose will be approximately 46-50 Gy.

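### Section 5.3.6 allows an additional boost of up to 4 Gy under a 70 Gy maximum, but Section 5.3.3 already prescribes 70 Gy to the same structures, so the two limits cannot both hold

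*Combined protocol and SAP*

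**What the plan says.** Section 5.3.3 sets the fractionation, "Treatment to the primary tumor and upper neck will be given at 2 Gy/fraction once each day, five days a week", and the total for the primary tumor and upper neck: "A total dose of 70 Gy/35 fractions/7 weeks will be delivered". It treats involved nodes the same way, "Clinically positive neck nodes should also receive a dose of 70 Gy/35 fractions given continuously for 7-8 weeks", and sums up: "Hence, the total dose to the primary tumor and clinically positive nodes will be 70 Gy".

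The other places that give a dose to gross disease agree. The abstract, the study schema and the Section 5 treatment plan all give 70 Gy. In the shrinking-field description of Section 5.3.4.2, "The third and final field reduction will occur at 60 Gy and continue to 70 Gy". For the IMRT primary target, Section 5.3.11.2 says "The dose will be 70 Gy at 2 Gy/ fractions".

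Section 5.3.6 then adds a further permission: "Additional boost doses may be given through reduced field to persistent tumor and/or clinically positive nodes, or to compensate for significant interruptions". Its limit is: "The additional boost dose should not exceed 4 Gy (i.e., 70 Gy maximum".

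Section 5.3.5 has a separate 4 Gy cap on a supplemental dose to involved nodes in the lower neck, with no maximum total beside it.

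**The concern.** The boost in Section 5.3.6 is described as additional, and it is aimed at tumor and involved nodes that Section 5.3.3 has already taken to 70 Gy. A boost on top of that dose cannot also stay within a 70 Gy maximum. The sentence presents the 4 Gy allowance and the 70 Gy ceiling as equivalent, and from the protocol's own base dose they are not.

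What is at stake is a prescribing limit. A radiation oncologist who wants to treat persistent disease or compensate for a long interruption would find one paragraph that both permits a boost and leaves no room for it. The matter also touches the study's outcomes in kind. The stage 2 primary endpoint is locoregional progression-free survival at 1 year (Section 11.1), and the events that drive the suspension rule in Section 11.4 are grade 3/4 mucositis and radiation dermatitis, both of which arise in the irradiated field. The dose permitted to the tumor should therefore be unambiguous and known.

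**Working it through.** **Inputs**

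- Fraction size 2 Gy, once daily, 5 days a week; 35 fractions over 7 weeks; total 70 Gy to the primary tumor and to involved nodes (Section 5.3.3).
- Field reductions at 50 Gy and 60 Gy, the last continuing to 70 Gy (Section 5.3.4.2).
- IMRT primary target 70 Gy (Section 5.3.11.2).
- Additional boost at most 4 Gy; stated maximum 70 Gy (Section 5.3.6).
- Lower neck 46–50 Gy if clinically negative (Section 5.3.3); supplemental dose to involved lower-neck nodes at most 4 Gy (Section 5.3.5).

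**Step 1. Reproduce the base dose.**

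- By fractions: 35 × 2 Gy = 70 Gy.
- By weeks: 7 weeks × 5 fractions × 2 Gy = 70 Gy.
- By shrinking fields: 50 + (60 − 50) + (70 − 60) = 70 Gy.

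The base dose reproduces exactly by all three routes.

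**Step 2. Try to reproduce the stated maximum after a boost.** Boosted total = base + boost = 70 + 4 = 74 Gy. The stated maximum is 70 Gy, so it is not reproduced. The gap is 4 Gy, or two fractions of 2 Gy; 4/70 = 5.7% of the prescribed dose.

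**Step 3. Hold the maximum fixed instead.** Boost available = maximum − base = 70 − 70 = 0 Gy. The permission then has no content for a patient who has received the full base dose.

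**Step 4. Look for a reading that makes the sentence true.**

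- A different base: 70 − 4 = 66 Gy, that is 66/2 = 33 fractions. No section gives 66 Gy as a base dose. The figure only shows what the sentence would require; it is not a suggestion.
- The lower neck: 46 + 4 = 50 Gy to 50 + 4 = 54 Gy, not 70 Gy. The lower neck also has its own boost sentence in Section 5.3.5.
- The IMRT planning text: the hot-spot and organ limits there are planning constraints, not a prescribed boosted total.
- The opening line of Section 5.3, which leaves radiation to institutional standard of care, sets no total.

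None of these resolves the conflict.

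**Step 5. A related mismatch.** Section 5.3.3 gives involved neck nodes 70 Gy. Adding the Section 5.3.5 supplement to the lower-neck dose gives only 50–54 Gy. The 46–50 Gy figure is stated for a clinically negative neck, so the sum is indicative, but the text does not say how involved lower-neck nodes reach 70 Gy under a 4 Gy cap. Reconciling Sections 5.3.3 and 5.3.6 alone would leave this open.

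**The case against.** The strongest reply is that 70 Gy is the only ceiling printed, and that every other statement of dose to gross disease also says 70 Gy. A prescriber who follows the written maximum cannot exceed it, so the practical result may be a boost allowance that does nothing rather than a higher dose. That is fair, and it tempers the safety concern: 74 Gy is a sum of two stated figures, not a dose that the protocol prints. It does not remove the contradiction, because the paragraph still grants an additional boost of a stated size for stated reasons.

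Scope is also uncertain. Section 5.3.6 sits in the conventional-technique text. IMRT is allowed under its own guidelines, which contain no boost provision. Whether 5.3.6 reaches IMRT patients is not stated, so the number of patients concerned is unknown.

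Three stronger conclusions are tempting, and the documents do not support them.

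- A reader might infer that the discrepancy changes locoregional control or in-field toxicity. The documents give no dose-response figure for a 4 Gy increment and no expected number of boosted patients. The 5.7% is a ratio of doses, not an effect size.
- A reader might infer that boosted patients are those most likely to fail locoregionally, so that the primary result is biased. That is clinically plausible, but no failure rate for persistent disease or interrupted treatment is given.
- A reader might infer that sites will treat to different doses. Section 11.3 names one conducting center. Section 5.3 does speak of participating institutions, but variation between sites is not shown. The ambiguity is better placed with individual prescribers.

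**Conclusion.** The inconsistency is real and can be seen from the text alone. From a 70 Gy base, a 70 Gy maximum leaves 0 Gy of boost, and a 4 Gy boost implies 74 Gy. The limit cannot be followed as written, and it should be corrected because it governs the dose given to patients.

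The conclusion rests on one reading: that the boost is added to the Section 5.3.3 dose in the same structures. Both the word additional and the targets named in Section 5.3.6 support this.

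The point goes no further. It is an internal inconsistency in a prescribing limit, not a demonstrated bias in the primary result or in the toxicity monitoring. Sample size, power and alpha do not depend on it.

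**What to change.** The sponsor, with its radiation oncologists, should reconcile Sections 5.3.3 and 5.3.6, together with 5.3.4.2 (final field reduction), 5.3.5 (the separate 4 Gy cap for involved lower-neck nodes) and 5.3.11.2 (IMRT dose), so that base dose, boost allowance and stated maximum agree. The text should also say whether Section 5.3.6 applies to patients treated with IMRT. Which dose is right is for the sponsor to decide.

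As a secondary step, any boost given should be recorded, with its dose and reason, and described alongside the primary result. Existing documents can carry this: the treatment record mentioned in Section 5.3.10 and the final treatment summary form in Section 12.3.2. Neither section currently names boosts as an item.

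The cost is a short protocol clarification and one added item on a form. No analysis changes.

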### 5.3.7 Dose Calculations

#### Photon Beam Portal Arrangements

Dose specification for two parallel-opposed coaxial equally-weighted beams is to be on the central ray at mid-separation of the beams.

Dose specification for two or more intersecting beams is at the intersection of the central ray of the beams.

For other complex treatment arrangements, dose is specified at the center of the clinical target volume.

Note: There may be several target volumes.

For a single anterior AP lower neck field, the prescribed dose will be delivered at a depth of 3.0 cm as determined by an off-axis "supraclavicular point". A deeper prescription point may be required if distance to the supraclavicular fossa is greater or with clinically involved nodes. When AP-PA fields are used to treat the lower neck, the dose shall be prescribed at the mid-separation of the two beams along the central ray.

### 5.3.8 Isodose Distributions

Isodose distribution at central axis is required. All treatment volumes and critical structures should be indicated. Complete isodose curves are required. Attempts should be made to keep the dose variation within the planning target volume to be within +/- 5% of the target dose.

### 5.3.9 Electron Beam Dose Specifications

The target dose shall be prescribed at the depth of maximum dose. The energy and field size shall be chosen so that the target volume is encompassed within 90% of the prescribed dose.

### 5.3.10 Time and Dose Modifications

Treatment interruptions are strongly discouraged. Treatment breaks must be clearly indicated in the treatment record when they occur. If the total treatment interruptions exceed ten treatment days, the treatment will be considered a protocol deviation. The interruption of radiation therapy for grade 4 mucositis/dermatitis/dysphagia is at the discretion of the treating oncologist.

The maximum permitted spinal cord dose is 45 Gy.

Mandibular osteoradionecrosis will rarely occur if pretreatment dental evaluation is conducted prior to radiation therapy treatment. Pretherapy extractions of badly diseased teeth should be carried out with conservation of restorable teeth when possible. If an extraction site in the mandible has to be included in the irradiated field, 10 to 14 days should be allowed for healing before the initiation of irradiation.

#### Radiotherapy Guidelines/IMRT

5.3.11 Intensity Modulated Radiation (IMRT) is allowed in the study.

5.3.11.1 Following are the proposed radiotherapy guidelines:

All patients will have immobilization devices with treatment planning based on Computerized Tomography (CT) information in treatment position. The CT slice thickness through target will be 3 mm.

CT, PET, and MRI data will be used to define the various targets and contour normal structures. MRI information will be used when indicated. Image fusion will be used to relate CT/MRI data when necessary.

The field sizes and arrangements will be at the discretion of the attending Radiation Oncologist. ICRU 50 guidelines will be used for various Tumor and Target Nomenclature.

The Gross Tumor Volume (GTV): All gross disease determined from clinical examination and radiographic studies (CT/PET/MRI).

The Clinical Target Volume (CTV): The area that potentially contains microscopic disease. Lymph node groups at risk of microscopic disease will be outlined as part of corresponding CTV. The margin between each GTV and corresponding CTV can vary from 0.2 cm to 2.5 cm depending upon the proximity to the critical and uninvolved structures.

The Planning Target Volume (PTV): Provides a margin around CTV to compensate for internal motion and set up errors. Typically a 5 mm margin may be used around CTV.

5.3.11.2 Radiation Target and Dose Specifications

The following is the definition of targets and their dose specifications.

Primary Target (PTV3): Includes PTV's of primary tumor and the lymph nodes containing disease. The dose will be 70 Gy at 2 Gy/ fractions.

Secondary Target (PTV2): Includes PTV's of area at moderate to high risk of microscopic disease i.e. first echelon nodes. The dose will be 60 Gy.

Tertiary Target (PTV1): Includes PTV's of areas that are at low risk of microscopic disease i.e. second echelon lymph nodes. The dose will be approximately 46-50 Gy.

#### Low Neck

The midjugular, low jugular, and supraclavicular nodes can be treated with IMRT or alternatively with an AP field that is beam split to the IMRT fields. Dose Volume Histograms (DVH) will be generated for each plan. Radiation doses will be as outlined above.

#### Treatment Planning

Either forward or inverse planning can be used in order to achieve the following:

The radiation dose will be prescribed to the isodose line that encompass 95% of PTV.

No more than 15% of the PTV will receive >110% of the prescribed dose.

The maximum dose within PTV does not exceed >25% of the prescribed dose.

No more than 1% of the tissue outside PTV will receive >110% of the prescribed dose.

No more than 1% of any PTV will receive < 93% of the prescribed dose.

Tissue heterogeneity correction is mandatory.

The planning priorities include critical normal structure constraints followed by prescription goals.

Normal Tissues: The appropriate normal organs will be contoured. Dose Volume Histograms (DVH) will be generated. An attempt will be made to keep the maximum radiation doses to the following organs as follows:

Brain Stems:	54Gy
Optic Nerve/Chiasm:	55 Gy
Spinal Cord:	45 Gy
Mandible/TM Joint:	70 Gy or 1 cc of the PTV not to exceed 75 Gy
Larynx	70 Gy

Parotid Glands: Attempt will be to achieve mean dose  $\leq$  26 Gy in at least one gland or at least 20cc of the combined volume of both parotid glands will receive < 20 Gy or at least 50% of the gland will receive < 30 Gy (should be achieved in at least one gland).

Other Normal Structures: Submandibular/sublingual glands, inner and middle ears, eye, lens will be considered low priority. The aim should be to decrease the doses as much as possible without compromising target.

5.3.12 Amifostine is not permitted.

5.3.13 Pilocarpine (Salagen) is allowed as per physician discretion. If used, all details must be recorded on the data forms.

#### 5.4 Salvage Surgery

Salvage surgery may be performed after radiation, if there is local and/or regional progression of disease.

Elective (planned) neck dissection or other surgery required for residual but not progressive disease will NOT be considered treatment failure.

Surgical removal (salvage) of the primary tumor: Directed biopsies at the site of the index lesions should not be performed in the absence of suspicion for relapse. Criteria for biopsy after radiation includes a persistent mucosal abnormality or imaging studies that are suspicious for persistent or recurrent disease.

Surgical removal (salvage resection) of the primary tumor should be performed if biopsy-proven cancer remains more than two months after completion of chemoradiotherapy. This will be considered progression of disease for the evaluation of the primary endpoint. The nature of the surgical resection should be dictated by the extent of tumor at the initial evaluation. The operation should be conducted using accepted criteria for primary surgical treatment of the cancer.

Neck dissection: A neck dissection is recommended if a palpable or worrisome radiographic abnormality persists in the neck 8 weeks after completion of therapy.

Cervical lymphadenectomy should encompass the original levels of lymph node involvement. Preservation of the accessory nerve, jugular vein, and sternomastoid muscle is encouraged if consistent with complete removal of all residual nodal disease; however, the extent of the neck dissection will be at the discretion of the surgeon.

#### 5.5 Supportive Care

All supportive measures consistent with optimal patient care will be given throughout the study.

##### Concomitant Drugs

The use of G-CSF, erythropoietin or amifostine is not allowed during radiotherapy. No other antitumor agents will be given during protocol therapy.

Prophylactic placement of a gastrostomy tube before treatment begins is at the discretion of the treating physician. Gastrostomy tube placement is strongly recommended in patients with significant dysphagia and weight loss at baseline.

Aggressive oral and skin care and analgesics are recommended.

The use of amifostine is not permitted. Pilocarpine (Salagen) is not encouraged during treatment but is allowed. If used, it should be recorded in the treatment forms.

## 6. ADVERSE EVENTS

This study will utilize the **NCI CTCAE version 4.0** for toxicity and Adverse Event (AE) reporting ([http://ctep.cancer.gov/protocolDevelopment/electronic\\_applications/ctc.htm](http://ctep.cancer.gov/protocolDevelopment/electronic_applications/ctc.htm)). All appropriate treatment areas should have access to a copy of the CTCAE version 4.0.

Infusion reactions should be graded according to allergic reaction/hypersensitivity. Caution must be exercised with every cetuximab infusion, as there were patients who experienced their first severe infusion reaction during later infusions.

### 6.1 Adverse Drug Reactions Due to Gene Therapy

Note: A patient has died while being treated on a gene therapy protocol. That protocol used very high amounts of virus directly injected into the liver and treated a very different disease with a different gene than the one used in this study. This gene therapy protocol does not use a virus. The underlying disease that this patient had also made him more susceptible to complications of the gene therapy.

#### Risk of Cancer

When retroviral vectors enter a normal cell in the body, the DNA of the vector inserts itself into the normal DNA in that cell; this process is called integration. Most integration is expected to cause no harm to the cell or to the subject. However, there is a chance that there may be some regions of the normal human DNA where integration of the viral vector's DNA may result in activation of neighboring genes. For example, if one of these genes were a growth factor, this may cause uncontrolled division of the cell, resulting in a cancer. This type of event has occurred in one animal study in mice where the vector integration site correlates with the occurrence of cancer in these mice.

More recently, the first reports of a similar event have been identified in two children who received a retroviral vector in an experimental gene transfer clinical trial for X-linked Severe Immunodeficiency (X-SCID) conducted in France, not under the jurisdiction of the United States Food and Drug Administration (FDA). While most of the children who participated in this clinical trial appear to have been cured of their disease, these two children developed leukemia (a form of cancer of the blood) approximately 30 and 36 months, respectively, after receiving the gene therapy treatment. These children had extensive testing done to determine the cause of the leukemia. A group of experts in this field looked at all the test results and concluded that the gene transfer caused the leukemia. These children appear to be responding to the treatment of his/her leukemia, but his/her long-term prognosis is unknown at this time.

The risk of another cancer, including leukemia, developing in subjects who participate in this study, is unknown; however, in contrast to the French study this protocol does not use a virus.

Soreness and/or bleeding at the injection site.

Local inflammation (redness or swelling and/or discomfort) at the injection site.

Fever, reactions at the injection site of the gene transfer, which could develop into local ulcers or sores that could get infected.

*Note:* Administration of cancer gene transfer has been used before, although this specific EGFR antisense study drug has not been previously given to cancer subjects. It is not known what impact this gene transfer will have on future conventional chemo/radiation treatments or future reproductive capabilities.

## 6.2 Reporting Adverse Events

All adverse events which are considered to be related to the research study must be reported to the UT Health Science Center Institutional Review Board. All serious adverse events that meet the UT Health Science Center Institutional Review Board's criteria for reporting can be found website at (<http://research.uthscsa.edu/irb/>).

### 6.2.1 Serious AE (SAE) means any untoward medical occurrence that at any dose:

- Results in **death**.
- Is **life-threatening**. (The term "life-threatening" in the definition of "serious" refers to an event in which the patient was at risk of death at the time of the event; it does not refer to an event, which hypothetically might have caused death if it were more severe).
- Requires inpatient **hospitalization or prolongation of present hospitalization** (see clarification in the paragraph below on planned hospitalizations).
- Results in **persistent or significant disability/incapacity**. Disability is defined as a substantial disruption of a person's ability to conduct normal life functions.
- Is a **congenital anomaly/birth defect**.

Is a **medically important event** that may not be immediately life threatening or result in death or hospitalization but may jeopardize the patient or may require intervention to prevent one of the other outcomes listed in the definition above, or involves suspected transmission via a medicinal product of an infectious agent. Examples of such medical events include allergic bronchospasm requiring intensive treatment in an emergency room or at home, blood dyscrasias or convulsions that do not result in inpatient hospitalization, or the development of drug dependency or drug abuse; any organism, virus, or infectious particle (e.g., prion protein transmitting Transmissible Spongiform Encephalopathy), pathogenic or non pathogenic, is considered an infectious agent.

6.2.2 NIH guidelines for reporting serious adverse events for trials involving gene transfer agents or recombinant DNA molecules are found at <http://www4.od.nih.gov/oba/rdna.htm>.

6.2.3 The PI will report SAEs on trials involving gene transfer agents or recombinant DNA

molecules to the IRB according to their requirements.

